Statistical Analysis Plan
CITN12-03 NCT01881867

Version 2.0 13Nov2018

Protocol: A Phase 2 Study of recombinant glycosylated human interleukin-7 (CYT107) after completion of standard FDA approved therapy with sipuleucel-T (Provenge®) for patients with asymptomatic or minimally symptomatic metastatic castration-resistant prostate cancer (mCRPC)

Statistical Analysis Plan
CITN12-03 NCT01881867

Version 2.0 13Nov2018

STATISTICAL CONSIDERATIONS

Study Design/Endpoints

The proposed clinical trial is a phase II, open-label, multicenter, randomized study of the administration of CYT107 after the completion of standard FDA-approved therapy with sipuleucel-T for patients with asymptomatic or minimally symptomatic mCRPC. Patients who have completed a standard course of sipuleucel-T will be randomly assigned to either observation or 10 µg/kg of subcutaneous CYT107 every week for 4 doses beginning 3 to 7 days after completing sipuleucel-T therapy. Day 0 is the day of the first injection of CYT107.

The first six patients randomly assigned to receive CYT107 will be followed for an additional 4 weeks prior to the study expanding past six patients, as a lead-in phase to ensure safety and tolerability of the selected CYT107 dose.

Treatment Schema

Cohort	CYT107 Dose	Frequency
1 - Observation	No CYT107 dose	-----
2 - CYT107	10 µg/kg	Days 0, 7, 14 and 21

IL-7 is expected to increase the peak and the persistence of the immune response. The persistence might be the most important for effective immunotherapy, i.e. increasing the “area under the curve”. Thus, the primary endpoint for sizing the trial will be quantification of T-cell responses to PA2024 measured at day 70 (week 11), 7 weeks after the last CYT107 injection.

T cell responses will be measured by interferon-gamma ELISPOT as the most quantifiably and reproducible assay. In the IMPACT study, 2 weeks after last sipuleucel-T administration, the background-subtracted mean PA2024 ELISPOT was 40 SFC/ 3×10^5 PBMC with a standard deviation of 69 based on n = 63. At 10 weeks after the last administration the background-subtracted mean PA2024 ELISPOT was 23 SFC/ 3×10^5 PBMC with a standard deviation of 36 based on n = 42. Participant leukapheresis samples from pre-and post-Provenge® vaccine will be used when possible to allow planned a more comprehensive evaluation of longitudinal vaccine responses.

Primary Endpoint:

The effect on the number and percentage of PBMC subsets and T lymphocyte subsets (i.e., CD4⁺ and CD8⁺ T cell naïve, effector memory, and central memory subsets, CD4⁺ Treg and activated CD4⁺ and CD8⁺ T cells) will be assessed using multiparameter flow cytometric analysis of whole blood. The PBMC immunophenotyping assay will quantify

Statistical Analysis Plan
CITN12-03 NCT01881867

Version 2.0 13Nov2018

the absolute number and proportion of T cells (both CD8+ and CD4+), NK cells (CD56+CD3-), NKT cells (CD56+CD3+), B cells (CD19+), monocytes (CD16+), dendritic cells (HLA-DR+ CD123+ or CD11c+), and CD122 (IL15R-beta)-expressing cells.

An additional panel will quantify the absolute number and proportion of memory and naïve T cell subsets using antibodies to CD45RA, CCR7 and CD28 of regulatory T cells using antibodies to CD127 and CD25, and the activation state of T cells using antibodies to PD-1, ICOS, and HLA-DR, among others. The absolute change in each parameter as well as variance in change over time for each patient (mean, median, and SE/SD) will be evaluated.

3. To determine whether CYT107 administration increases the vaccine-induced antigen-specific antibody immune responses to PAP and PA2024

IgM and IgG response to PAP and PA2024 will be measured by standard ELISA.

4. To quantify the effects of CYT107 on T-cell diversity

The T-cell repertoire will be characterized by T-cell receptor (TCR) deep sequencing and the analysis will be done with the Immunoseq Analyzer software ([name], with Adaptive Biotechnologies, Seattle).

5. To assess the effects of CYT107 on the immune competence of patients with advanced prostate cancer

Bystander antigen specific immune responses will be assessed to other ongoing and nascent antitumor responses (e.g., PRAME, NY-ESO-1 and/or p53), additional tumor antigens specific to prostate cancer (e.g., PSA and/or PSMA), and memory viral responses (influenza A and CEF) using the IFNg ELISPOT assay.

Thymic function will be assessed by measuring levels of T-cell receptor rearrangement DNA excision circles (TRECs).

6. To assess the clinical efficacy and tolerability of sipuleucel-T plus CYT107 compared with sipuleucel-T alone

Adverse events will be graded and reported using the National Cancer Institute (NCI) Common Terminology Criteria for Adverse Events (CTCAE) Version 4.0. Clinical efficacy will be assess differences in (1) overall survival, (2) PSA kinetics (3) progression free survival and, (4) circulating tumor cells (CTC). Progression free survival will be assessed by RECIST criteria for measureable disease by bone scans and radiographic criteria for non-measurable bony metastasis.

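### The SAP defines monocytes by CD16 alone, which would miss most monocytes and would usually count mainly NK cells

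*SAP*

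**What the plan says.** The relevant text is in the SAP, Analysis of Secondary Endpoints, item 2.

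- Numbers and percentages of PBMC and T-lymphocyte subsets "will be assessed using multiparameter flow cytometric analysis of whole blood". The sentence that follows begins "The PBMC immunophenotyping assay will quantify" and then lists the classes.
- Each class is to be reported as an absolute number and a proportion, beginning with "the absolute number and proportion of T cells".
- The list continues "NK cells (CD56+CD3-), NKT cells (CD56+CD3+), B cells (CD19"+), and then "monocytes (CD16+), dendritic cells (HLA-DR+ CD123+ or CD11c"+).
- A second panel covers memory and naïve T cells, "regulatory T cells using antibodies to CD127 and CD25, and the activation state of T cells using antibodies to PD-1, ICOS, and HLA-DR". Its marker list is open-ended, but it is described only for T-cell subsets and T-cell activation and does not redefine monocytes.
- The analysis is described as "The absolute change in each parameter as well as variance in change over time for each patient", summarised by mean, median and SE or SD.

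CD14 is not mentioned anywhere in the SAP.

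**The concern.** Leaving the gating tree to a laboratory manual is ordinary practice. Here, however, the SAP does name a marker for monocytes, and that marker does not identify them. CD16 marks most NK cells and a minor subset of monocytes; the usual general monocyte marker is CD14. This is general knowledge of cell markers and is not stated in the SAP.

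Two consequences follow if the rule is applied as written. The CD16-negative majority of monocytes is left out of the monocyte count, so a real CYT107 effect on them would not show there. And because NK cells sit in the same class unless something else removes them, a change in NK cells could be reported as a change in monocytes. The SAP analyses change in each parameter, presumes that CYT107 acts positively on all immune parameters, and makes no multiplicity adjustment for the non-primary endpoints. A rise in this class would therefore tend to be accepted under the wrong name.

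**Working it through.** The SAP gives no figure on this point, so there is nothing of its own to reproduce. The check asks what a CD16+ class contains, first by logic and then over a range of assumed frequencies.

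**Step 1: monocytes missed.** Let m be the fraction of monocytes that are CD16+. The class can hold at most m of all monocytes, so the fraction missed is 1 − m.

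- Assumed m = 5%: missed 95%.
- Assumed m = 10%: missed 90%.
- Assumed m = 20%: missed 80%.

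Any added condition (scatter, lineage exclusion, viability) only narrows the CD16+ set. It can remove other cells but cannot restore the CD16-negative monocytes. This result therefore does not depend on the unstated gates.

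**Step 2: composition inside a mononuclear gate.** Take granulocytes as already excluded and no NK exclusion. Let M be monocytes and N be NK cells as a percentage of PBMC, and let n be the fraction of NK cells that are CD16+.

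Monocyte share = M·m / (M·m + N·n)

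Assumed grid: M = 10, 20, 30; m = 5%, 10%, 20%; N = 5, 10, 15; n = 80%, 90%, 95%. That is 3 × 3 × 3 × 3 = 81 combinations.

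- Lowest (M = 10, m = 5%, N = 15, n = 95%): 0.5 / (0.5 + 14.25) = 3.4%.
- Median, which equals the central combination (M = 20, m = 10%, N = 10, n = 90%): 2 / (2 + 9) = 18%.
- Highest (M = 30, m = 20%, N = 5, n = 80%): 6 / (6 + 4) = 60%.

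The share is below half in 77 of the 81 combinations. The other four all have N = 5 and m = 20%, that is, few NK cells and many CD16+ monocytes.

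**Step 3: what this does to a measured change.** Use absolute counts in the same central ratio, again assumed: 400 monocytes/µL with 10% CD16+ and 200 NK cells/µL with 90% CD16+. The class is 40 + 180 = 220 cells/µL. Suppose NK cells rise by half and monocytes stay constant. The class becomes 40 + 270 = 310, an apparent monocyte increase of 90/220 = 41%. Suppose instead that the 360 CD16-negative monocytes double and nothing else moves. The class stays at 220 and shows no change.

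**The case against.** The best defence is that the bracketed markers are shorthand. T cells are listed by CD4 and CD8 without CD3, B cells by CD19 without exclusions, and nothing is said of scatter or doublets. The full gating may stand in a protocol or laboratory manual that is not at hand, and a monocyte scatter gate or a CD56 exclusion would remove most NK cells. This has force against step 2: the NK share applies only if no such gate is used. It does not answer step 1, since no extra gate recovers CD16-negative monocytes. CD16 may also be a slip for CD14; if so, the line is still wrong and a one-character correction settles it.

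It can also be said that overlapping classes are not an error in themselves, because the SAP never claims that they partition the cells, and that a randomised comparison of CD16+ cells remains valid for CD16+ cells. Both are true. The fault lies in the name given to the class and in the conclusion drawn under that name.

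Two stronger readings are tempting, and the document does not support them.

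- **Neutrophils.** Because the specimen is whole blood and neutrophils carry CD16, a reader might infer that the class would be almost entirely neutrophils. But the SAP calls these PBMC subsets and a PBMC assay, so the natural reading is a mononuclear gate.
- **Dendritic cells.** Because no lineage exclusion is written and many monocytes are HLA-DR+ CD11c+, a reader might infer that the dendritic-cell count is largely monocytes. The markers named there are proper positive markers. An unwritten exclusion is gating detail commonly left to a laboratory manual, so its absence is something to confirm and not an error in the SAP.

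**Conclusion.** The point holds for the monocyte definition. As written, the rule misses most monocytes: 80-95% if 5-20% are CD16+. Without NK exclusion it would usually count mainly NK cells, with a monocyte share of about 3-60% (median 18%) inside a mononuclear gate. It cannot be said that the class is always mostly other cells, since 4 of the 81 assumed combinations do not fall below half.

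The sizes rest on assumed frequencies and on general marker knowledge; the SAP supplies neither. The direction of the first result needs only that a minority of monocytes carry CD16.

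The importance is minor. Monocytes are a side entry under an objective about the character of the T-cell response. The PA2024 ELISPOT primary endpoint, the sample size and the T-cell readouts are unaffected.

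**What to change.** Check the line in item 2 against the panel actually run, then do one of the following.

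- **If CD14 was stained:** define monocytes as CD14+ within the mononuclear gate, and use CD16 only to separate monocyte subsets.
- **If CD14 was not stained:** report the class as CD16+ cells and draw no conclusion about monocytes from it. The comparison itself need not be withdrawn.

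In the same edit, confirm with the laboratory that the dendritic-cell gate (HLA-DR+ with CD123+ or CD11c+) excludes monocytes, and say so in a few words.

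The cost is a short wording change and a query to the laboratory, plus some re-gating of stored data if the monocyte class was in fact gated on CD16. Neither option needs new samples or a new antibody.

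### Flow-cytometry item 2 fixes a raw change score, names no arm contrast and does not adjust for baseline; ANCOVA on the baseline value would be more precise at little cost

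*SAP*

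**What the plan says.** The trial is randomised with a concurrent control. Under Study Design/Endpoints, patients "will be randomly assigned to either observation or 10 µg/kg of subcutaneous CYT107 every week for 4 doses".

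Item 2 of Analysis of Secondary Endpoints sets out to assess "The effect on the number and percentage of PBMC subsets and T lymphocyte subsets" by multiparameter flow cytometry. After listing the cell panels it gives one analysis sentence, which begins "The absolute change in each parameter as well as variance in change over time for each patient" and provides for summary by mean, median and SE/SD. The item names no contrast between arms, no test and no covariate.

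Two other places bear on it. The Primary Endpoint text presumes that the other immune endpoints will have about the same power to show a difference as the primary one. It also names the Mann-Whitney-Wilcoxon test as part of the analysis, without tying it to flow cytometry or saying whether it is applied to change or to the post-treatment value. Stratification Factors says that randomisation is stratified by prior treatment. No analysis in the SAP uses the stratum or a baseline value as a covariate.

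**The concern.** Item 2 is not silent on analysis. It chooses a quantity, the absolute change within each patient, and the summaries to go with it. Two things follow.

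- The sentence alone does not say how the observation arm enters. An analyst must infer the arm comparison from general remarks made elsewhere.
- If the change is compared between arms, subtracting the baseline is an inefficient way to use it. Subtraction forces a slope of 1 of the post-treatment value on baseline, whereas ANCOVA estimates that slope. Where baseline and follow-up are only moderately correlated, the change score carries baseline noise into the contrast.

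At stake is the precision of a sizeable set of secondary comparisons in a trial with 38 evaluable patients per arm, and whether the SAP's expectation of similar power for these endpoints is realistic for the quantity it has chosen.

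**Working it through.** **The plan's own figure.** The SAP gives no power for flow cytometry. For the primary ELISPOT comparison it states means of 47 and 23, SD 36 in both groups, 38 evaluable per arm, two-sided 0.05 and 80% power. The standardised effect is 24/36 = 0.667. The two-sample t-test (noncentral t) gives 81.8%, so the stated figure reproduces.

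**Variance of the arm contrast.** Let r be the correlation between baseline and follow-up, with equal variances at the two times. Relative to comparing post-treatment values alone (variance 1):

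- change score: 2(1 − r)
- ANCOVA on baseline: 1 − r²
- ratio, change score to ANCOVA: 2(1 − r)/(1 − r²) = 2/(1 + r)

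The SAP gives no r, so the values below are assumptions. The power columns borrow the primary endpoint's standardised effect of 0.667 with 38 per arm, for illustration.

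| r (assumed) | Change score variance | ANCOVA variance | Ratio | Power, change score | Power, ANCOVA |
|---|---|---|---|---|---|
| 0.3 | 1.40 | 0.91 | 1.54 | 68% | 85% |
| 0.5 | 1.00 | 0.75 | 1.33 | 82% | 91% |
| 0.7 | 0.60 | 0.51 | 1.18 | 96% | 98% |

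The change score therefore has 54%, 33% or 18% more variance. Equivalently, 38 patients per arm analysed by change give the precision of 38(1 + r)/2 = 24.7, 28.5 or 32.3 per arm analysed by ANCOVA. The approximation ignores the few degrees of freedom spent on covariates.

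**Against post-treatment values alone.** Since 2(1 − r) exceeds 1 only when r is below 0.5, the change score loses to a simple post-treatment comparison below 0.5 and beats it above. ANCOVA is at least as precise as either.

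**If variances are unequal.** With baseline SD s0 and follow-up SD s1, the change-score variance minus the ANCOVA variance is (s1² + s0² − 2r·s0·s1) − s1²(1 − r²) = (s0 − r·s1)². This is never negative, so the direction holds. It is zero when s0 = r·s1, so the size depends on the equal-variance assumption.

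**The case against.** The strongest reply is that the arms will be compared. The trial is randomised, the Primary Endpoint text speaks of power for the other endpoints and explains why they get no multiplicity adjustment, and it names a two-sample rank test. On that reading, item 2 only defines the quantity to be evaluated. This largely stands. A reader might infer from item 2 that the observation arm is ignored, but the SAP taken as a whole does not support that. What remains is that item 2 does not make the link itself.

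A reader might go further and infer that drift after sipuleucel-T will be mistaken for a CYT107 effect, pointing to the reference ELISPOT means of 40 at 2 weeks and 23 at 10 weeks. The document does not support this either:

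- Comparing change between arms removes drift common to both.
- The figures are ELISPOT counts, not cell subsets, and the SAP gives no drift figure for the subsets.
- The two means rest on different numbers of patients ("with a standard deviation of 69 based on n = 63" and "with a standard deviation of 36 based on n = 42"). Treated as independent samples, which is an assumption, the difference of 17 has SE √(69²/63 + 36²/42) = 10.3, a ratio of 1.65. No paired figure is given.
- The SAP presumes that CYT107 raises the immune measures. A fall would mask such an effect, not imitate it.

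It can also be said that choosing change over ANCOVA is a modelling preference. It is not an error of validity: a between-arm comparison of change is unbiased under randomisation. But the baseline value is needed to compute change in any case, so the precision is available without new data. The objection to a log scale for every parameter is fair, since the endpoints include percentages and rare subsets may give zeros. The fix allows for that.

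**Conclusion.** The point holds as an inexpensive improvement. Item 2 fixes a per-patient absolute change, does not tie it to a between-arm contrast, and the SAP has no baseline-adjusted model. If the arms are compared on raw change, the variance is 54%, 33% or 18% larger than under ANCOVA at correlations of 0.3, 0.5 or 0.7. These figures rest on assumed correlations, equal variances, and an analysis of means and not ranks. If r is well below 0.5, a raw change score would not deliver the similar power that the SAP presumes (68% at r = 0.3, for the same standardised effect).

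The finding does not extend to a planned single-arm analysis or to a demonstrated risk of drift being read as drug effect. These endpoints are secondary and the primary day-70 ELISPOT comparison is unaffected. Importance: low to moderate.

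**What to change.** Replace the analysis sentence in item 2 with wording such as:

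> Each parameter is compared between the randomised arms at the planned post-baseline visits by ANCOVA, or by a mixed model across visits, with the pre-CYT107 value (in the observation arm, the value at the corresponding visit) and the randomisation stratum as covariates. A log or rank transform is used where the data are skewed or contain zeros. Arm differences or ratios are reported with 95% confidence intervals. Per-patient change is summarised descriptively.

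If the Mann-Whitney-Wilcoxon test is meant for these endpoints, say so and say whether it is applied to change or to the post-treatment value.

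The cost is a change of SAP wording and slightly more analysis work. It needs no additional samples, visits or patients.
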